3.3. Other Endpoint(s)

The following exploratory endpoints are defined in this study:

- CCI
- Concentration of sisunatovir from paired samples obtained via microsampling compared to plasma sampling (if possible).

3.4. Baseline Variables

There are no baseline variables to be used as covariates or stratification factors in this study.

Baseline characteristics will be collected according to the schedule of activities (SoA) as specified in the protocol.

3.5. Safety Endpoints

The following data will be considered in standard safety summaries (see protocol for collection days, assessment procedures, and list of parameters):

- Adverse events (AE) / Serious adverse events (SAE)
- Laboratory tests data
- Vital signs data
- 12-lead ECG results

3.5.1. Adverse Events

Any adverse events occurring following start of treatment will be considered as treatment emergent adverse event (TEAE). If an AE starts on the same day as the first dose date, it will be considered treatment emergent unless the CRF data indicates otherwise via explicitly recording time for AE onset which was occurred before the first treatment dosing. Events

that occur during follow-up within the lag time of up to 28-35 days after the last dose of study intervention will be counted as treatment emergent and attributed to the last treatment taken. Events that occur during the washout period between study periods will be counted as treatment emergent and attributed to the previous treatment taken. The time period for collecting AEs ("active collection period") for each participant begins from the time the participant provides informed consent. The algorithm will not consider any events that started prior to the first dose date.

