8.4.1. Time Period and Frequency for Collecting AE and SAE Information

The time period for actively eliciting and collecting AEs and SAEs (“active collection period”) for each participant begins from the time the participant provides informed consent, which is obtained before undergoing any study-related procedure and/or receiving study intervention), through and including a minimum of 28 calendar days, except as indicated below, after the last administration of the study intervention.

Follow-up by the investigator continues throughout the active collection period and until the AE or SAE or its sequelae resolve or stabilize at a level acceptable to the investigator.

When a clinically important AE remains ongoing at the end of the active collection period, follow-up by the investigator continues until the AE or SAE or its sequelae resolve or stabilize at a level acceptable to the investigator and Pfizer concurs with that assessment.

For participants who are screen failures, the active collection period ends when screen failure status is determined.

If the participant withdraws from the study and also withdraws consent for the collection of future information, the active collection period ends when consent is withdrawn.

If a participant permanently discontinues or temporarily discontinues study intervention because of an AE or SAE, the AE or SAE must be recorded on the CRF and the SAE reported using the CT SAE Report Form.

Investigators are not obligated to actively seek information on AEs or SAEs after the participant has concluded study participation. However, if the investigator learns of any SAE, including a death, at any time after a participant has conducted the study participation, and they consider the event to be reasonably related to the study intervention, the investigator must promptly report the SAE to Pfizer using the CT SAE Report Form.

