10.3.1. Definition of AE

AE Definition

• An AE is any untoward medical occurrence in a patient or clinical study participant, temporally associated with the use of study intervention, whether or not considered related to the study intervention.• Note: An AE can therefore be any unfavorable and unintended sign (including an abnormal laboratory finding), symptom, or disease (new or exacerbated) temporally associated with the use of study intervention.

Events Meeting the AE Definition

• Any abnormal laboratory test results (hematology, clinical chemistry, or urinalysis) or other safety assessments (eg, ECG, radiological scans, vital sign measurements), including those that worsen from baseline, considered clinically significant in the medical and scientific judgment of the investigator. Any abnormal test results that meet any of the conditions below must be recorded as an AE:
• Is associated with accompanying symptoms;• Requires additional diagnostic testing or medical/surgical intervention;• Leads to a change in study dosing (outside of any protocol-specified dose adjustments) or discontinuation from the study, significant additional concomitant drug treatment, or other therapy.• Exacerbation of a chronic or intermittent preexisting condition, including an increase in either frequency and/or intensity of the condition.• New condition detected or diagnosed after study intervention administration, even though it may have been present before the start of the study.• Signs, symptoms, or the clinical sequelae of a suspected drug-drug interaction.• Signs, symptoms, or the clinical sequelae of a suspected overdose of either study intervention or a concomitant medication. Overdose per se will not be reported as an AE or SAE unless it is an intentional overdose taken with possible suicidal/self-harming intent. Such overdoses should be reported regardless of sequelae.

Events NOT Meeting the AE Definition

- Any clinically significant abnormal laboratory findings or other abnormal safety assessments that are associated with the underlying disease, unless judged by the investigator to be more severe than expected for the participant's condition.
- The disease/disorder being studied or expected progression, signs, or symptoms of the disease/disorder being studied, unless more severe than expected for the participant's condition.

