- Medical or surgical procedure (eg, endoscopy, appendectomy): the condition that leads to the procedure is the AE.
- Situations in which an untoward medical occurrence did not occur (social and/or convenience admission to a hospital).
- Anticipated day-to-day fluctuations of preexisting disease(s) or condition(s) present or detected at the start of the study that do not worsen.

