- The investigator will also consult the IB and/or product information, for marketed products, in their assessment.
- For each AE or SAE, the investigator **must** document in the medical notes that they have reviewed the AE or SAE and have provided an assessment of causality.
- There may be situations in which an SAE has occurred and the investigator has minimal information to include in the initial report to the sponsor. However, **it is very important that the investigator always make an assessment of causality for every event before the initial transmission of the SAE data to the sponsor.**
- The investigator may change their opinion of causality in light of follow-up information and send an SAE follow-up report with the updated causality assessment.
- The causality assessment is one of the criteria used when determining regulatory reporting requirements.
- If the investigator does not know whether or not the study intervention caused the event, then the event will be handled as “related to study intervention” for reporting purposes, as defined by the sponsor. In addition, if the investigator determines that an SAE is associated with study procedures, the investigator must record this causal relationship in the source documents and CRF, and report such an assessment in the dedicated section of the CT SAE Report Form and in accordance with the SAE reporting requirements.

Follow-Up of AEs and SAEs

- The investigator is obligated to perform or arrange for the conduct of supplemental measurements and/or evaluations, as medically indicated or as requested by the sponsor, to elucidate the nature and/or causality of the AE or SAE as fully as possible. This may include additional laboratory tests or investigations, histopathological examinations, or consultation with other healthcare providers.
- If a participant dies during participation in the study or during a recognized follow-up period, the investigator will provide Pfizer Safety with a copy of any postmortem findings, including histopathology.

- New or updated information will be recorded in the originally submitted documents.
- The investigator will submit any updated SAE data to the sponsor within 24 hours of receipt of the information.

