5.2. General Methods

Descriptive analyses will be performed. Some measures will be summarized using graphical representations.

Summaries by treatment will include summaries by administrated dose and fed/fasted condition, when applicable.

For binary or categorical variables, number of participants, numbers and percentages of participants meeting the categorical criteria will be presented in accordance with the sponsor reporting standards.

For continuous variables, the data will be summarized using the number of participants, mean, median, standard deviation (SD), minimum, and maximum in accordance with the sponsor reporting standards. For appropriate PK parameters, geometric mean and geometric coefficient of variation (%CV) will also be summarized.

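### The SAP's treatment-emergent rule has no worsening clause, so an AE record opened before first dose that worsens on drug, if kept as one record, is left out of the TEAE summaries

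*SAP*

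**What the plan says.** SAP 3.5.1 counts as treatment emergent any AE that occurs after the start of treatment. It treats a same-day onset as emergent unless a recorded time places it before dosing. It ends: "The algorithm will not consider any events that started prior to the first dose date". Nothing in the section mentions a change in severity, seriousness or frequency.

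Protocol 8.4.1 sets the start of active AE collection: it "begins from the time the participant provides informed consent". Screening may begin up to 28 days before first dose (Protocol 1.3), so a record can be opened well before any drug is given.

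Protocol 10.3.1 includes among events that are AEs: "Exacerbation of a chronic or intermittent preexisting condition, including an increase in either frequency and/or intensity of the condition". Among events that are not AEs it lists "Anticipated day-to-day fluctuations of preexisting disease(s) or condition(s) present or detected at the start of the study that do not worsen".

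On follow-up of an event already reported, Protocol 10.3.3 says: "New or updated information will be recorded in the originally submitted documents". The documents contain no instruction to open a new record when an existing AE gets worse.

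SAP 6.6.1 lists all AEs. The summaries (high-level, and by system organ class and preferred term) are of TEAEs only.

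**The concern.** A treatment-emergent definition is meant to separate what was present before drug from what appeared or got worse on it. The SAP's rule covers the first part and omits the second. Take mild nausea recorded on Day -1 that becomes moderate after dosing. If the site updates the existing record, the event still has a Day -1 start, and the rule removes it from the tables.

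AEs are a named secondary endpoint for safety and tolerability (SAP 2.2), and the TEAE tables are where a reader will look for them. The events at issue are those that got worse after dosing, which a tolerability summary most needs to show. This is a stated exclusion, so a programmer who follows the SAP faithfully will apply it.

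**Working it through.** The documents give no AE rate, and the sample size rests on a regulatory requirement (Protocol 9.5), so there is no planned figure to reproduce. The check is mainly a reading of the rules, case by case.

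**Case 1. A preexisting condition, not recorded as an AE, worsens on drug.** Protocol 10.3.1 makes the exacerbation an AE. Its onset is after first dose, so SAP 3.5.1 counts it as a TEAE. Nothing is lost.

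**Case 2. An AE record opened between consent and first dose worsens on drug.**
- If the site enters the worsening as a new record with its own start date, it is a TEAE.
- If the site updates the existing record, the start date stays before first dose. The last sentence of SAP 3.5.1 excludes it, and it appears only in the listing.

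**Case 3. An AE starts on Days 1-3 and worsens on or after the first Day 4 dose.** It is already a TEAE and stays in the overall count. The SAP does not say which phase it belongs to after worsening.

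Only the second branch of Case 2 loses an event.

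**Direction.** Adding a worsening clause can move records only from non-TEAE to TEAE. The count under the present rule is therefore never higher than under the amended rule.

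**Size.** With N = 12 (SAP 2.3, approximately), one participant is 1/12 = 8.3 percentage points. This is the most that one participant can move any single row, because a participant who already has a TEAE in that row is counted there anyway. For a row with no other events, with exact (Clopper-Pearson) 95% intervals:
- 0/12 = 0%, interval 0 to 26.5%
- 1/12 = 8.3%, interval 0.2 to 38.5%

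**How often it might arise.** Let p be the chance that a participant has a pre-dose AE record that worsens on drug. The documents give no value, so p is assumed over a range. P(at least one of 12) = 1 - (1 - p)^12.

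| Assumed p | Expected number, 12p | P(at least one of 12) |
|---|---|---|
| 1% | 0.12 | 11% |
| 2% | 0.24 | 21% |
| 5% | 0.60 | 46% |
| 10% | 1.20 | 72% |

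In healthy adults followed for at most a few weeks before dosing, the lower rows seem more plausible, but that is a judgement.

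**The case against.** The strongest reply is that the protocol already treats worsening as an AE, so it would be entered with an on-treatment onset and counted. That stands for Case 1. For a record already open it depends on how the site enters the change, and the instruction in Protocol 10.3.3 points, if anything, to updating the original. That instruction does not settle how the AE page handles a change in severity. The CRF completion requirements (Protocol 10.1.7) and the sponsor reporting standards (SAP 6.6.1) might require a new row, but neither document is reproduced here.

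Other safeguards also stand. All AEs are listed, and with about 12 participants a pre-dose event is easy to find there. SAEs in the collection period are reported to the sponsor whatever their TEAE status (Protocol 8.4.1.1). Liver enzymes are a poor example: elevations at screening are exclusionary (Protocol 5.2), and SAP 6.6.2 tabulates laboratory abnormalities with and without regard to baseline. No hypothesis or decision rule depends on the TEAE count.

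A reader might go further and infer that the SAP contradicts the protocol. It does not: the protocol defines an AE but gives no treatment-emergent rule, so there is none for the SAP to be narrower than.

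A reader might also infer that a Day 1-3 event worsening under twice-daily dosing is credited to the single dose, so that multiple-dose tolerability is undercounted. SAP 3.5.1 says only that "Events that occur during the washout period between study periods will be counted as treatment emergent and attributed to the previous treatment taken", which concerns where an event occurs and is silent on later worsening. SAP 6.6.1 states no split by phase, and SAP 5.2 offers one only conditionally: "Summaries by treatment will include summaries by administrated dose and fed/fasted condition, when applicable". An undercount would need both a split table and assignment by onset alone, and neither is stated for AEs.

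**Conclusion.** The point holds in a limited form. As written, SAP 3.5.1 leaves out of the TEAE summaries any AE record opened between consent and first dose that worsens after dosing and is kept as one record. The effect can only be to understate on-drug worsening, by up to 8.3 percentage points per affected participant in a given row. Whether any participant will be affected is unknown, and the number may be zero.

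The conclusion assumes that sites may update an open record when an event worsens, which the documents allow and do not rule out, and that the programmer applies the last sentence of SAP 3.5.1 literally. An actual undercount is not shown, for the study overall or for the multiple-dose phase. The handling of events that start on Days 1-3 and later worsen is a gap to clarify; it is not a demonstrated error.

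**What to change.** Replace the last sentence of SAP 3.5.1 with a rule to this effect: an event with onset before first dose is not treatment emergent unless its severity or seriousness increases on or after first dose; if it does, it is counted as a TEAE at the worsened severity.

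Have the CRF guidance record such worsening with its own start date, so that the rule can be programmed from the data.

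As a secondary clarification, state whether TEAE tables are split by single-dose and multiple-dose phase. If they are, apply the same worsening rule to events that start on Days 1-3 and worsen on or after the first Day 4 dose.

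The cost is a few sentences in the SAP, a line of CRF guidance and a small programming change, all best settled before database lock. Reported TEAE counts may be slightly higher. No extra participants, visits or procedures are needed.

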3.5.2. Laboratory Data

Safety laboratory tests will be performed as described in the protocol.

To determine if there are any clinically significant laboratory abnormalities, the haematological, clinical chemistry and urinalysis safety tests will be assessed against the criteria specified in the sponsor reporting standards. The baseline measurement is the value collected on Day -1 prior to the treatment start, or the last pre-dose measurement collected if the Day -1 measurement is not available.

3.5.3. Vital Signs

Supine blood pressure (BP), pulse rate (PR) and temperature will be measured at times specified in the SoA given in the protocol.

The baseline measurement is the predose measurement on Day 1 or the last predose measurement collected if the Day 1 measurement is not available.

The maximum increase from baseline will be calculated by first subtracting the baseline value from each post-dose measurement to give the change from baseline. The maximum of these values will then be selected, except in the case where a participant does not show an increase. In such an instance, the minimum decrease should be taken.

Similarly, the maximum decrease from baseline will be determined by selecting the minimum value of the changes from baseline. In cases where a participant does not show a decrease, the minimum increase should be taken.

3.5.4. Electrocardiograms

A 12-lead ECG will be obtained at specified day and timepoint as indicated in the SoA of the protocol. If not supplied, QTcF will be derived using Fridericia's heart rate correction formula:

$$QTcF = QT / (RR)^{(1/3)} \text{ where } RR = 60/HR \text{ (if not provided)}$$

The baseline value is the predose measurement on Day 1 or the last predose measurement collected if the Day 1 measurement is not available.

The maximum increase from baseline will be calculated by first subtracting the baseline value from each postdose measurement to give the change from baseline. The maximum of these values over the respective period will then be selected, except in the case where a participant does not show an increase. In such an instance, the minimum decrease should be taken.

4. ANALYSIS SETS (POPULATIONS FOR ANALYSIS)

Data for all participants will be assessed to determine if participants meet the criteria for inclusion in each analysis population prior to unblinding and releasing the database and classifications will be documented per standard operating procedures.

The following analysis set are defined in this study:

Participant Analysis Set	Description
Enrolled	"Enrolled" means a participant's, or their legally authorized representative's, agreement to participate in a clinical study following completion of the informed consent process and assignment to study intervention.
PK Concentration Analysis Set	The PK concentration analysis set is defined as all participants who take at least 1 dose of study intervention and in whom at least 1 plasma concentration value is reported.
PK Parameter Analysis Set	The PK parameter analysis set is defined as all participants who take at least 1 dose of study intervention and have at least 1 of the PK parameters of interest calculated.
Safety analysis set	All participants who take at least 1 dose of study intervention.

5. GENERAL METHODOLOGY AND CONVENTIONS

Final analysis will be performed after study participant data set release following the last participant last visit.

5.1. Hypotheses and Decision Rules

No statistical hypothesis will be tested in this study.

5.2. General Methods

Descriptive analyses will be performed. Some measures will be summarized using graphical representations.

Summaries by treatment will include summaries by administrated dose and fed/fasted condition, when applicable.

For binary or categorical variables, number of participants, numbers and percentages of participants meeting the categorical criteria will be presented in accordance with the sponsor reporting standards.

For continuous variables, the data will be summarized using the number of participants, mean, median, standard deviation (SD), minimum, and maximum in accordance with the sponsor reporting standards. For appropriate PK parameters, geometric mean and geometric coefficient of variation (%CV) will also be summarized.

5.3. Methods to Manage Missing Data

5.3.1. Safety Data

For the analysis of safety endpoints, the sponsor data standard rules for imputation will be applied.

5.3.2. Pharmacokinetic Data

Concentrations Below the Limit of Quantification

In all data presentations (except listings), concentrations below the limit of quantification (BLQ) will be set to zero. In listings BLQ values will be reported as “<LLQ”, where LLQ will be replaced with the value for the lower limit of quantification.

Deviations, Missing Concentrations and Anomalous Values

In summary tables and plots of mean/median profiles, statistics will be calculated having set concentrations to missing if one of the following cases is true:

1. A concentration has been collected as ND (ie, not done) or NS (ie, no sample).
2. A deviation in sampling time is of sufficient concern or a concentration has been flagged as anomalous by the pharmacokineticist.

Note that summary statistics will not be presented at a particular time point if more than 50% of the data are missing.

An anomalous concentration value is one that, after verification of bioanalytical validity, is grossly inconsistent with other concentration data from the same individual or from other participants. For example, a BLQ concentration that is between quantifiable values from the same dose is considered as anomalous. Anomalous concentration values may be excluded from PK analysis at the discretion of the PK analyst or pharmacokineticist.

PK Parameters

Actual PK sampling times will be used in the derivation of PK parameters.

If a PK parameter cannot be derived from a participant's concentration data, the parameter will be coded as NC (ie, not calculated). (Note that NC values will not be generated beyond the day that a participant discontinues).

In summary tables, statistics will be calculated by setting NC values to missing; and statistics will be presented for a particular treatment with ≥ 3 evaluable measurements. PK parameter analyses will not be performed for a particular parameter if more than 50% of the data are NC.

If an individual participant has a known biased estimate of a PK parameter (e.g. due to an unexpected event such as vomiting before all the compound is adequately absorbed from the gastrointestinal tract), this will be footnoted in summary tables and will not be included in the calculation of summary statistics or statistical analyses.

